NHL	Non-Hodgkin lymphoma
OS	Overall survival
PR	Partial response
PS	Performance status
PET	Positron emission tomography
K	Potassium
PQC	Product Quality Complaint
PD	Progressive disease
PFS	Progression free survival
SPM	Second primary malignancy
SAE	Serious adverse event
Na	Sodium
TTNT	Time to next anti-lymphoma treatment
TNF- α	Tissue necrosis factor- alpha
VTE	venous thromboembolism

1. BACKGROUND

Follicular lymphoma (FL) is the most common indolent Non-Hodgkin lymphoma (NHL) and is characterized by high response rates to initial therapy coupled with relapse, and is considered incurable with standard treatment options. Prognosis has been associated with age, stage, disease burden, lactate dehydrogenase, hemoglobin, and presence of B-symptoms.[1, 2] The majority of patients with FL present with advanced stage disease and are often asymptomatic. In addition to clinical prognostic factors, biologic or immune signature prognostic factors have been reported.[2-4] FL is characterized by high incidence of BCL-2 deregulation, t(14:18) and forms the basis for PCR assessment of minimal residual disease (MRD) in FL.[5] Despite high response rates, most patients with FL will succumb to their disease and clinical outcomes remain heterogeneous.

Though a number of management strategies have been utilized for patients with previously untreated FL, it was not until incorporation of rituximab, a monoclonal antibody to CD20 antigen that improvement in overall survival was achieved.[6] Based on the Stanford experience, there was no significant change in the natural history of FL from the 1960's through the early 1990's, despite modifications of the chemotherapy regimens[7]. The most commonly prescribed frontline strategy for FL in the United States in the modern era is rituximab in combination with chemotherapy.[8] Despite high response rates[9, 10], and median PFS exceeding 5 years with the addition of maintenance rituximab[11], chemotherapeutic immunotherapy is not considered curative in FL, as patients continue to relapse. In addition, the side effect profile associated with cytotoxic therapy[12] raises the question, what is the optimal frontline strategy for FL?

Lenalidomide, a thalidomide derivative, is a second generation immunomodulatory drug, proposed to have multiple mechanisms of action, including beneficial effects on both tumor and microenvironment. Lenalidomide has been associated with TNF- α inhibitory, and T-cell costimulatory, and antiangiogenic activities.[13] The molecular action of lenalidomide, involves its binding to protein targets cereblon, Ikaros, and Aiolos[14-17], and subsequent effects on protein ubiquitination and degradation.[18] Lenalidomide as an immunomodulator is an interesting approach to the management of FL given the most successful therapy to date for FL has been incorporation of immune therapy (rituximab).

Most frequently reported adverse events reported during clinical studies with lenalidomide in oncologic and non-oncologic indications, regardless of presumed relationship to study medication include: anemia, neutropenia, thrombocytopenia and pancytopenia, abdominal pain, nausea, vomiting and diarrhea, dehydration, rash, itching, infections, sepsis, pneumonia, urinary tract infection, upper respiratory infection, atrial fibrillation, congestive heart failure, myocardial infarction, chest pain, weakness, hypotension, hypercalcemia, hyperglycemia, back pain, bone pain, generalized pain, dizziness, mental status changes, syncope, renal failure, dyspnea, pleural effusion, pulmonary embolism, deep vein thrombosis, cerebral vascular accident, convulsions, dizziness, spinal cord compression, syncope, disease progression, death not specified and fractures.

Proprietary Information of MD Anderson

The combination of lenalidomide plus rituximab has synergistic effects against lymphoma, as demonstrated in vitro and in animal models, by enhancing rituximab-induced apoptosis and rituximab-dependent NK cell-mediated cytotoxicity.[19-22] Based on the observed efficacy of lenalidomide combined with rituximab in relapsed/refractory indolent NHL[23], and the expectation of synergy between these agents, our group completed a phase 2, single arm study to evaluate the efficacy and safety of lenalidomide and rituximab in patients with untreated, advanced-stage indolent NHL, demonstrating efficacy and safety of the combination.[24] Overall response rate (ORR) in our study was 90% with a complete response rate of 63%, and 75% of patients remained in remission at 36 months. Of the evaluable patients with FL (N=46), 45 had an ORR, 98%. 40 patients with FL had a CR or unconfirmed CR (87%), and three-year PFS estimates were 78.5%.[24] Similar findings were demonstrated by a phase 2, multi-center study investigating the combination in previously untreated patients with indolent NHL.[25] Based on these findings, a phase 3, randomized international registration study comparing the efficacy of lenalidomide and rituximab versus chemoimmunotherapy for previously untreated FL patients (RELEVANCE; NCT01476787) has completed enrollment, results are eagerly awaited, but not anticipated for a few years.

Another compelling approach to management of indolent NHL is targeting a key cellular pathway or attribute specific to tumor cells. The B-cell receptor (BCR) is the unique molecular fingerprint of each B-cell and signals emanating from the BCR act through downstream pathways to direct development, proliferation, and survival of normal B cells. The BCR and downstream pathways are also frequently manipulated by B-cell malignancies. As a result, targeted agents inhibiting BCR-activated signaling pathways have been successfully translated into the clinical setting.[26, 27] Ibrutinib, an orally available, selective kinase inhibitor irreversibly binds Cys-481 residue on Bruton tyrosine kinase. In a phase 1 study of ibrutinib in relapsed/refractory B-cell malignancies, ibrutinib was well tolerated; the maximum tolerated dose was not reached.[28] Notable was an ORR of 60% in evaluable patients. These findings prompted multiple phase 2 studies [26, 29], demonstrating efficacy of ibrutinib and led to FDA approval in relapsed mantle cell lymphoma patients who have received at least one prior therapy, chronic lymphocytic leukemia or small lymphocytic lymphoma patients who have received at least one prior therapy, chronic lymphocytic leukemia or small lymphocytic lymphoma patients with deletion 17p, and Waldenstrom's macroglobulinemia. Ibrutinib is being studied for the treatment of several other illnesses and its use in this study is investigational.

Commented [CP1]: GCDO: align with current label – add Small Lymphatic Lymphoma.

With the evolving knowledge of the BCR pathway and tumor microenvironment, exploiting insights into the oncogenic pathways appears to be a promising approach. The combination of lenalidomide and ibrutinib has reported synergism in vitro.[14] In a cereblon-dependent fashion, lenalidomide downregulates IRF4 and SPIB, transcription factors that prevent interferon β production by repressing IRF7 and amplify NF- κ B signaling by transactivating CARD11.[14] Blockade of BCR signaling using ibrutinib also downregulates IRF4 and synergizes with lenalidomide in killing activated B-cell like diffuse large B-cell lymphoma cell lines, suggesting an attractive therapeutic strategy.

A phase 1 study of ibrutinib in combination with rituximab and lenalidomide in previously untreated stage II-IV FL patients has been completed (NCT01829568). The primary objective was to determine the recommended phase 2 doses of ibrutinib and lenalidomide for combination with rituximab in previously

Proprietary Information of MD Anderson

untreated FL. Secondary objectives were to determine the pharmacokinetics of ibrutinib and its major metabolite (PCI-45227) when combined with lenalidomide and rituximab and to determine the pharmacodynamics of basophil activation and BTK occupancy in PBMCs over a 24-hour period of ibrutinib when given in combination with lenalidomide and rituximab. Treatment consisted of dose escalations of lenalidomide and ibrutinib and a fixed dose of rituximab (375 mg/m²). Once the maximum tolerated dose was reached, there was to be an expansion cohort of ten additional patients. These ten patients were to receive the fixed dose of rituximab, and the recommended phase 2 doses of ibrutinib and lenalidomide. Patients received lenalidomide PO on days 1-21 of a 28 day cycle for 18 cycles, and ibrutinib PO on days 1-28 until disease progression. Patients received rituximab by IV infusion on day 1, day 8, day 15, and day 22 of cycle 1. Four remaining doses of rituximab were to be given at week 13, week 21, week 29, and week 37.

22 subjects with FL were enrolled at different dose levels.

Dose Level	Ibrutinib (mg)	Lenalidomide (mg)	Rituximab (mg/m ²)
-2	280	5	375
-1	420	10	375
0	420	15	375
1	560	15	375
2	560	20	375

The dose escalation schema was standard for a 3+3 design. If dose level 0 is shown to be too toxic (i.e. has > 1/6 DLTs), dose de-escalation was to be continued until finding a dose level with 0/3 or 1/6 DLT. If the dose level has 1/6 DLT this dose was to be selected as the MTD. If the dose level has 0/3 DLT, another 3 patients were to be added at this level. If the level has ≤ 1/6 DLT with the addition, of 3 patients, it will be selected as the MTD. If the dose level has > 1/6 DLTs, dose de-escalation was to continue. DLT was defined as any non-hematologic or hematologic toxicity listed below that occurs during the first cycle of treatment. Toxicities were graded according to the National Cancer Institute Common Terminology Criteria for Adverse Events (NCI CTCAE), version 4.0. Patients were to be evaluated once per cycle for any adverse events.

Non-hematologic dose-limiting toxicity was defined as any of the following: any Grade 3 or 4 non-hematologic toxicity (excluding: Grade 3 rash that resolves to < Grade 2 within 10 days with systemic corticosteroid treatment, fatigue, anorexia, nausea, fever without neutropenia, tumor lysis syndrome); grade 3 rash that does not resolve to < Grade 2 within 10 days with corticosteroid treatment; any grade Stevens-Johnson syndrome or toxic epidermal necrolysis; grade 3-4 bullous dermatitis; failure of any Grade 3 or 4 non-hematologic toxicity (as defined above) to resolve or recover to baseline level after delaying the next dose by more than 2 weeks; AST or ALT ≥ 3 x ULN in combination with a total bilirubin ≥ 2 x ULN. Hematologic dose-limiting toxicity was defined as any of the following: any Grade 4 hematologic toxicity, except for grade 4 neutropenia ≤ 7 days; grade 4 neutropenia > 7 days; grade 3 or

Proprietary Information of MD Anderson

4 neutropenia complicated by fever $\geq 38.5^{\circ}\text{C}$ or infection; grade 4 thrombocytopenia (must be repeated same day by a separate peripheral blood draw to confirm toxicity); grade 2-3 thrombocytopenia complicated by hemorrhage.

The preliminary safety data that has not been reported or published suggests the combination is tolerable. Of 22 subjects, 8 developed a Grade 1 or 2 rash, and 8 subjects developed a Grade 3 rash; rash was not considered a DLT in this study unless the rash did not resolve to < Grade 2 within 10 days with corticosteroid treatment. In addition, rash was associated with allopurinol in several cases and with Bactrim (sulfamethoxazole and trimethoprim) in 1 case. No cytokine storm reactions were seen. As a result of this approach, in the CTEP/A051103 study, no DLTs were seen and no MTD was identified. The rashes were manageable with temporary holding of ibrutinib and lenalidomide, concomitant therapy with corticosteroids and/or antihistamines, and discontinuation of potential contributors such as allopurinol if applicable. The maximum dose of lenalidomide given was the highest planned dose of 20 mg.

In the phase 2 study of lenalidomide and rituximab in previously untreated FL [24], the most common hematologic adverse event was neutropenia (25% grade 3, 10% grade 4), however, febrile neutropenia was infrequent (<1%), upper respiratory infections were generally mild (21% grade 2, 2% grade 3). Common non-hematologic adverse events were fatigue (90% all grades, 5% grade ≥ 3), pain or myalgia (82% all grades, 9% grade 3), nausea or vomiting (61% all grades, 0 grade ≥ 3), rash (58% all grades, 7% grade 3), diarrhea (50% all grades, 0 grade ≥ 3), and constipation (52% all grades, 0 grade ≥ 3). Less frequent non-hematologic grade 1 or 2 adverse events included cough (44%), dizziness (43%), edema (43%), peripheral neuropathy (36%), infusion reaction (13%), and thyroid test abnormalities (23%). Second malignancies were reported in 5 patients. No deaths occurred on study as a result of toxicity.

The MTD of ibrutinib in phase 1 studies has not been reached. [28] The most common (>20%) non-hematologic adverse events associated with ibrutinib have generally been mild (Grade 1 or 2) and include diarrhea (50%), fatigue (41%), nausea (31%), peripheral edema (28%), dyspnea (27%), constipation (25%), upper respiratory infection (23%), vomiting (23%), and decreased appetite (21%). Grade ≥ 3 hematologic toxicities include neutropenia (16%), thrombocytopenia (11%), and anemia (10%). [26] Four patients in the phase 2 study that led to the FDA indication for ibrutinib in relapsed/refractory mantle cell lymphoma had subdural hematomas (Grade 1 in 1 subject, Grade 2 in 1 subject, Grade 3 in 2 subjects); all were associated with falls, head trauma, or both. [26] Though infrequent, additional non-traumatic bleeding complications associated with ibrutinib have been reported including gastrointestinal bleeding and hematuria.

Marginal zone lymphoma is a less frequent indolent NHL and is most commonly managed similar to follicular lymphoma given limited prospective data to guide routine practice. We included untreated marginal zone and small lymphocytic lymphoma in the phase 2 study of rituximab in combination with lenalidomide. [30] We enrolled 30 subjects with untreated marginal zone lymphoma subjects, 67% achieved a CR and 22% a PR with an ORR of 89%. Median PFS was 53.8 months in the subjects with marginal zone lymphoma. The median PFS in follicular lymphoma had not been reached suggesting the

Proprietary Information of MD Anderson

combination of lenalidomide and rituximab was most promising in follicular lymphoma, but still associated with favorable outcomes in marginal zone lymphoma.

Gene expression profiling studies though limited by small number of samples have identified a set of markers with differential expression in nodal marginal zone lymphoma compared with follicular lymphoma. [31, 32] The nodal marginal zone lymphoma signature was associated with deregulated pathways including BCR signaling, interleukins (IL-2, IL-6, IL-10), integrin signaling (CD40), and cell survival pathways (MAPKs, tumor necrosis factor, transforming growth factor- β , and NF- κ B), conferring a survival advantage in nodal marginal zone lymphoma. Inactivation of the A20 gene is also a common genetic aberration in marginal zone lymphoma which may contribute to lymphomagenesis via constitutive NF- κ B signaling. [33] Alteration in lymphoma biology and signaling may explain the differences observed with therapeutic outcomes in follicular and marginal zone lymphoma. Targeting the BCR pathway may be even more attractive in marginal zone lymphoma. A phase II trial PCYC-1121 (NCT01980628) examined single agent ibrutinib in 63 patients with marginal zone lymphoma with at least one prior therapy. The results are eagerly awaited, but are anticipated to be favorable given a supplemental new drug application has been submitted to the FDA for use of ibrutinib as treatment for patients with marginal zone lymphoma. Therefore, extending the eligibility of this study to untreated marginal zone lymphoma is warranted to examine the safety and efficacy of rituximab, lenalidomide and ibrutinib in untreated marginal zone lymphoma.

With the prolonged natural history of FL, identifying optimal endpoints or surrogates for overall survival for frontline studies is an evolving field. In an analysis of the National LymphoCare Study, previously untreated patients with FL who experienced progressive disease within 2 years of initial treatment were identified as a high risk group, “early progressors”. [34] Early progression was dramatically associated with poor overall survival, hazard ratio (HR) =13.3 (95% confidence interval [CI] 7.94-22.4). After adjusting for FLIPI score, early progression was associated with an increased risk of death (HR=15.4, 95% CI 9.6-24.7). This suggests that a landmark progression-free survival at 2 years may predict for a high risk population and discern a difference in outcomes. Another proposed efficacy endpoint includes the complete response rate at 120 weeks or 30 months. [35] Both approaches serve as surrogate endpoints for overall survival.

We are proposing a novel frontline, open-label, phase 2 clinical trial for previously untreated patients with FL and marginal zone lymphoma, a non-cytotoxic approach based on sound scientific rationale with emerging clinical endpoints. The proposed study builds on our experience with frontline rituximab in combination with lenalidomide which has demonstrated similar efficacy in single-arm phase 2 studies with historical comparison to rituximab in combination with chemotherapy, with the addition of ibrutinib as a mechanism of targeting the BCR pathway in addition to the tumor and microenvironment. We aim to explore the efficacy and safety of the novel combination of rituximab, lenalidomide, and ibrutinib in previously untreated patients with FL and marginal zone lymphoma.

2. STUDY OBJECTIVES

Proprietary Information of MD Anderson

2.1 Primary Objective

The primary objective is to evaluate the efficacy of ibrutinib combined with rituximab and lenalidomide in patients with previously untreated FL and marginal zone lymphoma (determined by PFS at 2 years).

2.2 Secondary Objectives

The secondary objectives are:

- To evaluate the efficacy of ibrutinib combined with rituximab and lenalidomide in subjects with FL and marginal zone lymphoma as assessed by CR at 120 weeks, ORR, DOR, EFS, TTNT, and OS.
- To evaluate the safety and tolerability of ibrutinib combined with rituximab and lenalidomide in previously untreated subjects with FL and marginal zone lymphoma.

2.3 Exploratory Objective

The exploratory objectives are to evaluate prognostic and mechanistic biomarkers relative to treatment outcomes.

3. STUDY DESIGN

3.1 Description of Study

This is an open-label, Phase 2, single center study designed to assess the efficacy and safety of ibrutinib combined with rituximab and lenalidomide in previously untreated subjects with FL and marginal zone lymphoma. The study will include approximately 60 subjects in one treatment arm.

Once a patient provides written informed consent, the patient may enter the screening period, which is permitted to last up to 4 weeks. During the screening period, the patient will undergo safety and other assessments to determine eligibility for the study. The patient eligibility will be based on investigator assessment. The patient will enter the treatment period once the patient has fulfilled the required assessment in the screening period. The treatment period for each patient starts with study day 1 of cycle 1. The treatments will be given as described in Section 7. The patients will receive protocol-specified treatments, until:

- 1) Relapse or progression of disease
- 2) Withdrawal of consent,
- 3) Unacceptable toxicity, or
- 4) End of study.

Upon completion of the required treatments, the patient will enter the three-year follow-up period.

During the follow-up period, patients will be followed for disease progression, next lymphoma treatment, and OS.

3.2 Endpoints

3.2.1 Primary Endpoint:

Proprietary Information of MD Anderson

Progression-free survival (PFS) at 2 years as assessed by the investigator

3.2.2 Secondary Endpoints:

Efficacy:

- Complete response rate ([CR], based on Cheson, Lugano classification 2014) at 120 weeks as assessed by the investigator
- Overall response rate (CR + partial response [PR]) based on Cheson, Lugano 2014 as assessed by the investigator
- Duration of response (DOR)
- Event free survival (EFS)
- Time to next anti-lymphoma treatment (TTNT)
- Overall survival (OS)

Safety:

- Frequency, severity, and relatedness of treatment-emergent adverse events (AEs)
- Frequency of treatment-emergent AEs requiring discontinuation of study drug or dose reductions

3.2.3 Exploratory Endpoints:

- Immunophenotyping of PBMCs to determine alteration in immune cell subsets
- Identification of signaling pathways or biomarkers that predict sensitivity or resistance by gene expression profiling
- Determination of alteration of cytokines and chemokines

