9.3.3 Secondary Efficacy Endpoints

- CR rate at 120 weeks (± 4 weeks) will be determined by the PI (Cheson, Lugano classification 2014). The number and percentage of subjects with a CR at 120 weeks will be tabulated.
- ORR (CR + PR) will be assessed by the investigator based on Cheson, Lugano 2014. The number and percentage of subjects with an ORR will be tabulated. The best ORR will be recorded.
- DOR will be measured from the time by which measurement criteria for CR or PR, whichever is recorded first, is met until death or the first date by which progressive disease is documented. Subjects who are progression free and alive at the time of clinical cut-off or have unknown

status will be censored at the last tumor assessment. Subjects with no baseline disease assessment will be censored on cycle 1, day 1. Non-responders will be excluded from the analysis for DOR. Kaplan-Meier methodology will be used to estimate event-free curves, median, and 95% CI.

- EFS will be measured from the date of cycle 1, day 1 to the date of first documented progression, transformation to diffuse large B-cell lymphoma, initiation of new anti-lymphoma treatment, or death. Kaplan-Meier methodology will be used to estimate event-free curves, median, and 95% CI.
- TTNT will be measured from the date of cycle 1, day 1 to the date of first documented administration of any anti-lymphoma treatment (chemotherapy, radiotherapy, immune therapy, radioimmunotherapy, or other experimental therapy). Kaplan-Meier methodology will be used to estimate event-free curves, median, and 95% CI.
- OS will be measured from the date of cycle 1, day 1 to the date of death regardless of cause. For subjects who have not died, subjects will be censored at the time of last contact. Kaplan-Meier methodology will be used to estimate event-free curves, median, and 95% CI.

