9.4 Handling of Missing Data

Subjects lost to follow up will be included in the statistical analyses up to the point of their last evaluation or contact.

Data for subjects without disease progression or death will be censored at the date of the last tumor assessment and before the date of initiation of alternative anticancer therapy. Subjects with no post-baseline assessment will be censored on cycle 1, day 1.

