9.5 Determination of Sample Size

The primary endpoint is PFS. It is expected that the experimental regimen will achieve better efficacy compared to the standard of care for this population. We will enroll a total of 60 patients with an accrual rate of 4 patients per month. All patients will be followed for at least 3 years or until death. The final analysis will be performed when the last patient is followed for 3 years. When the sample size is 60, a two-sided 95% CI for the PFS rate at 2 years will extend 0.106 from the observed rate for an expected rate of 77% (nQuery Advisor 7.0).

Proprietary Information of MD Anderson

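### Time to next treatment is estimated by Kaplan-Meier with treatment as its only event, so the proportion retreated is slightly overstated if any patient dies untreated

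*Combined protocol and SAP*

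**What the plan says.** The endpoint list in section 3.2.2 only names the endpoint: "Time to next anti-lymphoma treatment (TTNT"). The definition and method are in section 9.3.3: "TTNT will be measured from the date of cycle 1, day 1 to the date of first documented administration of any anti-lymphoma treatment", followed by "Kaplan-Meier methodology will be used to estimate event-free curves, median, and 95% CI". Death is not part of the definition, and no censoring rule is given for this endpoint.

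The neighbouring endpoints treat death explicitly. PFS (9.3.2.1) and DOR (9.3.3) count it as an event. The EFS definition ends with "initiation of new anti-lymphoma treatment, or death". OS has its own censoring sentence: "For subjects who have not died, subjects will be censored at the time of last contact".

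Section 9.4 adds two general rules. One reads "Subjects lost to follow up will be included in the statistical analyses up to the point of their last evaluation or contact". The other reads "Data for subjects without disease progression or death will be censored at the date of the last tumor assessment and before the date of initiation" and goes on to name alternative anticancer therapy. Neither says how a death without further treatment enters TTNT.

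**The concern.** Kaplan-Meier treats a censored patient as someone who could still have the event later. A patient who has died cannot start another treatment. With treatment as the sole event, censoring at death passes that patient's weight to those still at risk, as if the patient would have gone on to treatment at their rate. The complement of the curve then exceeds the proportion who actually receive further treatment.

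In a single-arm trial the absolute estimate is the whole result for this endpoint, so its meaning should be clear. The label in 9.3.3 adds to the difficulty: a reader will take an event-free curve for next treatment as the share alive and untreated, which it is not.

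The second rule in section 9.4 is a separate hazard. Applied literally to TTNT, it would censor a patient who starts new therapy without documented progression just before the event that TTNT is meant to record. It would also end follow-up of event-free patients at the last tumor assessment, although treatment status is known up to the last contact.

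**Working it through.** **The plan's own precision figure.** Section 9.5 says that, with 60 patients, "a two-sided 95% CI for the PFS rate at 2 years will extend 0.106 from the observed rate for an expected rate of 77"%. Check: 1.96 × √(0.77 × 0.23 / 60) = 0.1065, which agrees with 0.106. It concerns PFS. The plan states no precision figure for TTNT.

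**How a death without retreatment is handled.**
- 9.3.3: the event is treatment only, so this death is not an event.
- 9.4, first rule: it covers loss to follow-up, which a known death is not.
- 9.4, second rule: it covers patients without progression or death, so it does not apply.
- What remains under Kaplan-Meier is censoring at death. The plan does not write this. It follows from the definition and the method.

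**Inputs for the size.** The documents give neither a death rate nor a retreatment rate, so both are assumptions, taken as constant hazards.
- Next treatment, h_t: 0.08 to 0.13 per year. The upper value is close to −ln(0.77)/2 = 0.131, the hazard implied by the expected 2-year PFS in 9.5.
- Death without further treatment, h_d: 0.01 to 0.03 per year.
- Horizon: 4 years. Twelve 28-day cycles are 336 days, about 11 months. With 3 years of follow-up after the last dose, a patient who completes treatment has about 47 months from Cycle 1, Day 1.

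**Formulas.**
- One minus Kaplan-Meier, with deaths censored: 1 − exp(−h_t·t)
- Cumulative incidence of next treatment: h_t/(h_t + h_d) × [1 − exp(−(h_t + h_d)·t)]

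**Results at 4 years.**

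| h_t | h_d | 1 − KM | Cumulative incidence | Excess (points) |
|---|---|---|---|---|
| 0.08 | 0.01 | 27.4% | 26.9% | 0.5 |
| 0.10 | 0.02 | 33.0% | 31.8% | 1.2 |
| 0.13 | 0.03 | 40.5% | 38.4% | 2.1 |

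Middle row: 1 − exp(−0.40) = 0.330; (0.10/0.12) × [1 − exp(−0.48)] = 0.833 × 0.381 = 0.318.

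At 2 years the same grid gives an excess of 0.1 to 0.6 points. In patients, 0.5 to 2.1 points of 60 is about 0.3 to 1.3.

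**Sensitivity.** Set h_t at 0.131 or half of it, and the risk of untreated death by 4 years at 2% to 15% (the risk if no one were retreated). The 4-year excess then runs from 0.2 to 2.9 points. With no untreated deaths it is zero.

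**The case against.** The strongest case against the point is that it matters little. TTNT is one of six secondary efficacy endpoints, with no test or decision rule. The sampling error is far larger than the bias: at 67% with 60 patients, 1.96 × √(0.67 × 0.33 / 60) is about 12 points. The 0.131 hazard also comes from PFS, which already counts deaths, so adding a death hazard to it double-counts them and the upper end of the range leans high. All of this stands, and it limits the point to a minor one.

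Three stronger readings are tempting, and the documents do not support them.

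- **A reader might infer that untreated deaths, including toxic ones, escape the efficacy results.** They do not. PFS, DOR, EFS and OS all count death, and section 9.6 deals with treatment-related death separately. Nor would cumulative incidence count these deaths against the regimen: in the middle row it falls from 33.0% to 31.8%, which looks slightly better.
- **A reader might take the gap between the Kaplan-Meier curve and the share alive and untreated as the bias.** With h_t = 0.10 and h_d = 0.02, these are exp(−0.40) = 67.0% and exp(−0.48) = 61.9% at 4 years. But the second is a different quantity, which TTNT as defined does not claim to estimate. The gap argues against the event-free label. It does not measure error in the proportion retreated.
- **A reader might extend the figures to 5 years, where the excess grows.** Few patients get there. Accrual takes 60/4 = 15 months, so the longest follow-up is about 47 + 15 = 62 months. Only patients enrolled in roughly the first 2 months, about 8, could pass 60 months.

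**Conclusion.** The point holds in a limited form. As 9.3.3 is written, a death without further treatment can only be censored, and one minus Kaplan-Meier then overstates the proportion who receive further anti-lymphoma treatment. The direction is certain once any patient dies untreated while others remain at risk of treatment. The size depends on the assumed hazards and on their being constant over time; within the main range it is small beside the sampling error. The conflict between TTNT and the therapy-censoring rule in 9.4 needs no numerical assumption and should be settled in the same edit. The primary endpoint and the sample size are unaffected.

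**What to change.** In section 9.3.3, replace the Kaplan-Meier sentence for TTNT with text along these lines:

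*The cumulative incidence of next anti-lymphoma treatment will be estimated by the Aalen-Johansen method, with death before such treatment as a competing event, and reported with 95% CI at 2 and 4 years. Patients alive without further treatment will be censored at last contact. The section 9.4 rule on censoring before alternative anticancer therapy does not apply to this endpoint.*

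Do not call the resulting curve event-free. If the share alive and untreated is also wanted, report it separately as a named composite, time to next treatment or death, for which Kaplan-Meier is suitable.

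The cost is a few sentences and standard software. No new data are needed, because sections 7.3 and 7.3.1 already collect survival and later therapy. The downside is that the estimate is less directly comparable with published TTNT results based on Kaplan-Meier.
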